2.1. Objectives

To compare the efficacy and safety of the administration of TA-7284 100 mg once a day for 104 weeks to those of placebo in type 2 diabetes mellitus patients with Stage 3 diabetic nephropathy (overt nephropathy).

2.2. Study Design

Multicenter, randomized, double-blind, placebo-controlled, parallel-group, comparative study

Definitions of Periods

Periods	Definitions
Screening period	The period from the first day of the screening period until the completion of the scheduled tests on the first day of the run-in period, 4 weeks at most.
Run-in period	The 2-week period from the completion of the scheduled tests on the first day of the run-in period until the completion of the scheduled tests on the first day of the treatment period. The run-in period will be a single-blind period, and a placebo will be administered.
Treatment period	The period from the completion of the scheduled tests on the first day of the treatment period until the completion of the scheduled tests on the last day of the treatment period (Week 104 of the treatment period or the day of treatment period discontinuation). The treatment period will be a double-blind period, and TA-7284 100 mg tablets or a placebo will be administered.
Follow-up observation period	The 4-week period from the completion of the scheduled tests on the last day of the treatment period. No investigational product will be administered in the follow-up observation period. If a patient discontinues from the study before the treatment period, then no follow-up observation period will be needed.

2.3. Randomization Procedures

Subjects will be randomly assigned in a 1:1 ratio to the TA-7284 100 mg tablet group or the TA-7284 tablet placebo group based on stratified randomization, with eGFR on the first day of the run-in period as the stratification factor (≥ 30 and < 45 , ≥ 45 and < 60 , ≥ 60 and < 90).

2.4. Assessment Time Point

2.4.1. Test/Observation Schedule

Parameter	Time point a)	Screening Period b) (4 weeks max.)		Run-in Period (2 weeks)		Treatment Period (104 weeks)														Follow-up observation period (4 weeks)													
		Date of informed consent acquisition	First day of the screening period	First day of the run-in period	First day of the treatment period (Week 2 of run-in period)	Week of the treatment period	Week of the treatment period	Week 12 of the treatment period	Week 16 of the treatment period	Week 20 of the treatment period	Week 24 of the treatment period	Week 28 of the treatment period	Week 32 of the treatment period	Week 36 of the treatment period	Week 40 of the treatment period	Week 44 of the treatment period	Week 48 of the treatment period	Week 52 of the treatment period	Week 56 of the treatment period	Week 60 of the treatment period	Week 64 of the treatment period	Week 68 of the treatment period	Week 72 of the treatment period	Week 76 of the treatment period	Week 80 of the treatment period	Week 84 of the treatment period	Week 88 of the treatment period	Week 92 of the treatment period	Week 96 of the treatment period	Week 100 of the treatment period	At discontinuation	Week of the follow-up observation period	Up to discontinuation
VISIT	V1	V1	V2	V3	V4	V5	V6	V7	V8	V9	V10	V11	V12	V13	V14	V15	V16	V17	V18	V19	V20	V21	V22										
Telephone follow-up																																	
Allowable window c)	—	—	—	—	—	—	—	—	—	—	—	—	—	—	—	—	—	—	—	—	—	—	—	—	—	—	—	—	—	—			
Informed consent acquisition	●																																
Subject baseline characteristics	●	●	●	●																													
Run-in period investigational product administration d)					↔																												
Treatment period investigational product administration d)						↔																											
Investigation of treatment adherence	●	●	●	●	●	●	●	●	●	●	●	●	●	●	●	●	●	●	●	●	●	●	●	●	●	●	●	●	●	●			
Height						●																											
Weight						●																											
Vital sign						●																											
Standard 12-lead ECG						●																											
Pregnancy test e)						●																											
Clinical laboratory tests f)g)						●																											
eGFR g)						●																											
Urine ACR (first morning void urine) h)	•i)					●																											
HbA1c						●																											
Fasting blood glucose						●																											
Fasting urine glucose/creatinine ratio						●																											
Renal function biomarker						●																											
Investigation of adverse events k)	●	●	●	●	●	●	●	●	●	●	●	●	●	●	●	●	●	●	●	●	●	●	●	●	●	●	●	●	●	●			
Investigation of hypoglycemia (SMBG, survey form l)						↔																											

- On scheduled visit days, subjects will fast (including juice and alcohol) for at least 10 hours starting on the night before, and will come to the hospital in the morning with an empty stomach (except for on the first day of the screening period, at the visit at Week 4 of the follow-up observation period, and at discontinuation). However, patients will be allowed to drink water and other beverages that do not contain any calories.
- The screening period will be at most 4 weeks long.
- The first day of the treatment period will be the starting point for calculating the run-in and treatment periods, and the final assessment day in the treatment period will be the starting point for calculating the follow-up observation period (including for cases who discontinued from the study).
- Investigational product will start being administered on the first day of the run-in period and on the first day of the treatment period. Subjects will come in for the scheduled study visits without taking the investigational product.
- Pregnancy tests will be required for all females of childbearing potential.
- During the treatment period, urine glucose tests performed at the study sites will be prohibited.
- If a patient has an eGFR < 15 mL/min/1.73 m², or if the patient's serum creatinine value more than doubles compared to the average of the values on the first day of the run-in period and the first day of the treatment period, then the measurement will be performed at least 30 days, and preferably within 60 days, after the assessment time point at which this criterion will be met. If there is no scheduled visit during this period, then one is to be scheduled if possible.
- Collect first-morning void urine samples on 3 days within a one-week period that includes the scheduled visit day.
- If the urine ACR does not satisfy the inclusion criterion, retesting may be performed during the screening period if the (sub)investigator judges it to be medically

appropriate. Furthermore, no restrictions will be placed on the number of retests that may be performed.

[figure not shown]
- j) Only erythropoietin will be measured.
- k) Serious adverse events will be investigated from informed consent acquisition up until Week 4 of the follow-up observation period. Other adverse events will be investigated from after the start of the administration of the treatment period investigational product up until Day 14 of the follow-up observation period.
- l) The instructions on blood glucose self-measurement (SMBG) and on completing the hypoglycemia symptoms survey form will be given on the first day of the run-in period. Blood glucose self-measurements will be performed whenever possible when the patient experiences symptoms of hypoglycemia.

2.5. Sample Size Justification

300 subjects (150 subjects per group) as the number of subjects who will start the treatment period

Rationale

3. Endpoints

3.1. Efficacy Endpoints

3.1.1. Primary endpoint

Proportion of subjects achieving a 30% decline in the eGFR (The proportions of subjects at the end of the treatment period with a decline of 30% in the eGFR or more compared to the average of the values on the first days of the run-in and treatment periods)

3.1.2. Secondary endpoints

- (1) Proportion of subjects achieving a 40% decline in the eGFR (The proportions of subjects at the end of the treatment period with a decline of 40% in the eGFR or more compared to the average of the

values on the first days of the run-in and treatment periods)

- (2) The change and percent change in the eGFR at each assessment time point compared to the average of the values on the first days of the run-in and treatment periods
- (3) Composite endpoint of end-stage renal disease (ESRD), doubling of serum creatinine, renal death, and cardiovascular (CV) death
- (4) Composite endpoint of CV death and hospitalized congestive heart failure
- (5) Composite endpoint of CV death, non-fatal myocardial infarction, and non-fatal stroke
- (6) Hospitalized congestive heart failure
- (7) Composite renal endpoint of end-stage renal disease (ESRD), doubling of serum creatinine, and renal death
- (8) CV death
- (9) All-cause death
- (10) The CV composite endpoint of CV death, non-fatal myocardial infarction, non-fatal stroke, hospitalized congestive heart failure, and hospitalized unstable angina
- (11) Percent change from the first day of the treatment period in urine ACR (first morning void urine) at each assessment time point
- (12) Change from the first day of the treatment period in the HbA1c at each assessment time point
- (13) Change from the first day of the treatment period in fasting blood glucose at each assessment time point
- (14) Change from the first day of the treatment period in blood pressure (systolic blood pressure, diastolic blood pressure) at each assessment time point
- (15) Change and percent change from the first day of the treatment period in the lipid levels (HDL-C, fasting neutral lipids) at each assessment time point
- (16) Change and percent change from the first day of the treatment period in body weight at each assessment time point
- (17) Change from the first day of the treatment period in the fasting urine glucose/creatinine ratio at each assessment time point

3.2. Safety Endpoints

- (1) Adverse event
- (2) Hypoglycemia
- (3) Clinical laboratory test values
- (4) Standard 12-lead ECG
- (5) Vital signs

4. Definitions of Derived Variables

4.1. BMI

$$\text{BMI (kg/m}^2\text{)} = \text{Body weight (kg)}/\{\text{Height (m)}\}^2$$

The number of digits displayed will consist of the values rounded off to the first decimal point. Furthermore, the height and weight from the first day of the treatment period will be used.

4.2. Duration of Illness of the Primary Disease (Stage 3 Diabetic Nephropathy)

Duration of illness (in years) of the primary disease (Stage 3 diabetic nephropathy)

$$(\text{First day of the treatment period} - \text{Time of diagnosis of the primary disease} + 1)/365.25$$

The number of digits displayed will consist of the values rounded off to the first decimal point. If only the month is known for the time of onset, then the date will be reclassified as the fifteenth of the month for the purposes of this calculation. Also, if only the year is known, then the date will be reclassified as July 1.

4.3. Duration of Illness of Diabetes

Duration of illness of diabetes (in years)

$$(\text{First day of the treatment period} - \text{Diagnosis date of diabetes mellitus} + 1)/365.25$$

The number of digits displayed will consist of the values rounded off to the first decimal point. If only the month is known for the time of onset, then the date will be reclassified as the fifteenth of the month for the purposes of this calculation. Also, if only the year is known, then the date will be reclassified as July 1.

4.4. Blood Pressure (Systolic Blood Pressure, Diastolic Blood Pressure)

The median of 3 measured values will be used. If only 2 measured values are available, then the mean of these 2 values will be used, and if only 1 measured value is available, then this value will be used. These values will be displayed rounded off to the first decimal place.

4.5. Change and Percent Change

4.5.1. Parameters other than the eGFR

- Change

Change = Value at the measurement time point in question – value on the first day of the treatment

period

- Percent Change

Percent change = $[(\text{Value at the measurement time point in question} - \text{value on the first day of the treatment period}) / \text{Value on the first day of the treatment period}] \times 100$

The values will be displayed rounded off to the first decimal place.

4.5.2. eGFR

- Change

Change = eGFR value at the measurement time point in question – Mean of the eGFR value on the first day of the run-in period and the eGFR value on the first day of the treatment period

- Percent Change

Percent change = $[(\text{eGFR value at the measurement time point in question} - \text{Mean of the eGFR value on the first day of the run-in period and the eGFR value on the first day of the treatment period}) / \text{Mean of the eGFR value on the first day of the run-in period and the eGFR value on the first day of the treatment period}] \times 100$

The values will be displayed rounded off to the first decimal place.

4.6. Duration of Investigational Product Administration

4.6.1. Duration of Investigational Product Administration in the Run-in Period

For completers: Duration of investigational product administration in the run-in period (in days) = (First day of the treatment period – 1) – First day of the run-in period + 1

For discontinuations: Duration of investigational product administration in the run-in period (in days) = Day of discontinuation – First day of the run-in period + 1

4.6.2. Duration of Investigational Product Administration in the Treatment Period

For completers: Duration of investigational product administration in the treatment period (in days) =

(Day of the visit at Week 104 of the treatment period – 1) – First day of the treatment period + 1

For discontinuations: Duration of investigational product administration in the treatment period (in days) = Day of discontinuation – First day of the treatment period + 1

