9.2.2 Treatment Adherence

The (sub) investigator will at each subject visit investigate the subject's treatment adherence based on the number of tablets of the investigational product that remain and through questioning of the subject, and will record in the case report form the day the investigational product was first taken, the amount prescribed, the amount returned, the remaining drug, and the day on which the investigational product was last taken. Furthermore, if the subject has not taken the investigational product for 7 or more days in a row, the (sub) investigator will enter the date that this period began and the reason therefor in the case report form.

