12.2 Discontinuation Procedures

The (sub) investigator will take the appropriate actions for any subject who is discontinued from the study and promptly notify a monitor that the subject has been discontinued. The (sub) investigator will perform the tests and observations scheduled for discontinuation within 7 days of the treatment period discontinuation.

The follow-up observation period begins once the treatment period has been discontinued.

The (sub) investigator will record the date of discontinuation and the reason for discontinuation in the case report form. Furthermore, if the study is discontinued because of an adverse event, the term of the event that resulted in discontinuation will be recorded in the case report form. The date of discontinuation is the day on which evaluations on discontinuation (evaluation day) are performed or, when evaluations on discontinuation are not possible, the day on which the decision to discontinue the

subject was made.

For subjects for whom the observations/tests that should have been conducted at discontinuation could not be conducted, and for subjects who did not visit the study site following discontinuation, the reason(s) therefor, and the courses of the subjects following discontinuation, will be determined through follow-up investigations performed through written correspondence or telephone calls, and the information obtained will be recorded.

The (sub) investigator or a clinical research coordinator will whenever possible collect the Hypoglycemia Symptom Survey Forms of subjects who do not visit to the study site by, for example, having the subjects mail them back.

13. Statistical Analysis

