5.1. Efficacy Analysis Sets

(1) Efficacy Analysis Sets

1) FAS

The analysis sets consisting of all randomized subjects other than the following constitute the FAS.

- Subjects who were not type 2 diabetes mellitus patients with Stage 3 diabetic nephropathy (overt nephropathy)
- All subjects who did not take the investigational product at all
- All subjects for which no post-randomization efficacy data are available

2) PPS

The PPS is the FAS, minus the following subjects.

- Subjects who have deviated from the inclusion criteria
- Subjects who have met the exclusion criteria
- Subjects who have violated the stipulations about the prohibited concomitant drugs
- Subjects with a rate of compliance with the investigational product of 75% or lower
- Subjects with treatment periods shorter than 52 weeks

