Treatment period discontinuation		The day of treatment period discontinuation	Within 7 days of the day of treatment period discontinuation
Week 4 of the follow-up observation period		Week 104 of the treatment period (or the day of treatment period discontinuation)	28 to 42 days after the last day of the treatment period

*1: The first day of the run-in period should be within 4 weeks of the first day of the screening period.

*2: The first day of the treatment period is the day of the initial prescription of the treatment period investigational product.

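### For subjects who stop early, SAP 4.6.2 counts drug administration up to the discontinuation evaluation (or decision) day instead of the last dose, which overstates exposure and lowers computed compliance

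*SAP*

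**What the plan says.** SAP 4.6.2 has two formulas for the duration of administration in the treatment period.

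- Discontinued subjects: "Day of discontinuation – First day of the treatment period + 1".
- Completers: "Day of the visit at Week 104 of the treatment period – 1) – First day of the treatment period + 1" (the opening bracket stands just before the quoted words). One day is taken off, so the Week 104 visit day is not counted.

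The SAP does not say what the day of discontinuation is. Protocol 12.2 does: "The date of discontinuation is the day on which evaluations on discontinuation (evaluation day) are performed". If those evaluations are not possible, it is the day on which the decision to discontinue was made. Earlier in the same section, the investigator is told to "perform the tests and observations scheduled for discontinuation within 7 days of the treatment period discontinuation", which treats discontinuation as a separate and earlier event.

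Protocol 9.2.2 has the case report form record "the day on which the investigational product was last taken". No readable rule in the SAP uses that date.

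The 4.6.2 duration is the quantity summarised in SAP 7.5.1 and the denominator of compliance in SAP 4.7.2. SAP 5.1 removes from the PPS subjects with compliance of 75% or lower, and also "Subjects with treatment periods shorter than 52 weeks". SAP Table 6.2 accepts discontinuation data "Within 7 days of the day of treatment period discontinuation".

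**The concern.** A quantity described as duration of administration should stop when administration stops. For a subject who stops tablets and is evaluated some days later, 4.6.2 goes on counting until the evaluation. If no evaluation takes place, it counts to the decision day, which need not be the last dosing day either.

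Completers and discontinued subjects are also measured differently. Protocol 8.6.1 and note d of the test schedule have subjects attend scheduled visits before taking that day's tablet. The completer formula allows for this and the discontinuation formula does not.

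At stake are the exposure summary and its categories (7.5.1), the compliance figures (4.7.2 and 7.5.2), and through them the PPS 75% rule. In addition, Protocol 12.2 uses discontinuation in two senses. A programmer therefore cannot tell from the text which date anchors the 7-day window in Table 6.2 or ends the treatment period for the PPS 52-week rule.

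**Working it through.** The plan states no figure that depends on these definitions, so there is nothing to reproduce. The check is day arithmetic.

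**Inputs**
- Duration formulas: SAP 4.6.2.
- Meaning of the discontinuation date, and the planned 7 days to evaluation: Protocol 12.2.
- Compliance = (tablets prescribed − tablets returned) / duration × 100: SAP 4.7.2.
- PPS limits, compliance above 75% and treatment period of at least 52 weeks (52 × 7 = 364 days): SAP 5.1.
- Exposure categories with cuts at 13, 26, 52 and 78 weeks: SAP 7.5.1.

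**Assumptions.** One tablet is taken daily from the first day until the stop, all unused tablets are returned, and the evaluation takes place. Let g be the number of days from last dose to evaluation. The documents do not give g.

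**Step 1: same visit, two formulas.** Take a visit 363 days after the first day (treatment day 364).
- Completer formula: (363 − 1) + 1 = 363 days.
- Discontinuation formula: 363 + 1 = 364 days.

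The formulas differ by 1 day. For a subject who attends undosed and takes no further tablet (g = 1), that day is not a dosing day.

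**Step 2: general excess.** SAP duration = dosing days + g, so the excess is g days. For an evaluation on treatment day 364:

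| g (days) | Dosing days | Weeks on drug | SAP duration | SAP compliance |
|---|---|---|---|---|
| 0 | 364 | 52.0 | 364 days, 52.0 weeks | 100.0% |
| 1 | 363 | 51.9 | 364 days, 52.0 weeks | 363/364 = 99.7% |
| 7 | 357 | 51.0 | 364 days, 52.0 weeks | 357/364 = 98.1% |
| 28 (longer than planned; illustrative) | 336 | 48.0 | 364 days, 52.0 weeks | 336/364 = 92.3% |

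The row g = 0 applies only if a tablet was taken on the evaluation day. With g = 7, a subject with 51.0 weeks of drug moves from the category of 26 to under 52 weeks into that of 52 to under 78 weeks.

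**Step 3: compliance after a short treatment.** The relative effect grows as treatment gets shorter. With 28 daily tablets and g = 7, SAP compliance is 28/(28 + 7) = 80.0%, although no tablet was missed before the stop. Such a subject is outside the PPS because of the 52-week rule, but appears in the compliance table of 7.5.2.

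**Step 4: reach into the PPS 75% rule.** For a subject with a 364-day treatment period and g = 7, SAP compliance equals compliance up to the last dose multiplied by 357/364. It falls to 75% when compliance up to the last dose is 75 × 364/357 = 76.5%. Within the planned gap, only subjects above 75% and up to about 76.5% can be excluded because of the definition. For longer treatment periods the band is narrower.

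**The case against.** The strongest reply is that little depends on this. Exposure in 7.5.1 is descriptive, and the PPS is a secondary set whose handling the sponsor finalises by database lock. Membership of the full analysis set does not use 4.6.2. Safety person-years have their own definition in SAP 4.13. All of that stands. It is also fair to say that counting untaken days before formal discontinuation as non-compliance is a defensible convention. It does not, however, make those days administration, which is what 4.6.2 says it measures.

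A reader might infer three stronger points, which the documents do not support.

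- **That the 7-day window in Table 6.2 excludes nothing.** This follows only if its reference day is always the evaluation day. The 7-day instruction in Protocol 12.2 treats discontinuation as an earlier event, and Protocol 8.2.5 has the date of discontinuation recorded in connection with stopping the investigational product. On that reading the window works. What remains is an ambiguous anchor.
- **That subjects with less than 52 weeks of drug enter the PPS in error.** The rule refers to the treatment period, a defined term ending at Week 104 or on the day of treatment period discontinuation. It does not refer to dosing time or cite 4.6.2. A subject with a 52-week treatment period meets the rule as written. With the planned gap, the shortfall in drug is at most about one week.
- **That eGFR drawn more than 7 days after the last dose should be dropped.** SAP 6.2.1 assigns values by time window and does not call them on-treatment. Removing observed values is an estimand choice. In the primary analysis it would replace in-window observations with imputed ones.

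**Conclusion.** The point holds for exposure and compliance. SAP 4.6.2 ends administration on a date that Protocol 12.2 defines without reference to the last dose. It also includes, for discontinued subjects only, a final visit day that is removed for completers. The result is overstated exposure in 7.5.1 and lowered compliance under 4.7.2.

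The size is 1 day to about 1 week per discontinued subject. This assumes that the subject attends undosed and that the evaluation follows the last dose within the planned 7 days. Longer gaps give a larger excess, day for day, but the documents do not show that they occur. The effect on the PPS 75% rule is confined to subjects close to that limit.

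The two meanings of discontinuation in Protocol 12.2 are a separate ambiguity that needs a stated answer. Nothing here changes membership of the full analysis set or the safety person-years of SAP 4.13.

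**What to change.** In SAP 4.6.2, end administration for discontinued subjects on the date the investigational product was last taken, as recorded under Protocol 9.2.2. Keep the present rule as fallback when that date is missing. Use this duration in 7.5.1 and as the denominator in 4.7.2.

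Reconcile the two uses of treatment period discontinuation in Protocol 12.2. State in the SAP, before database lock, which date anchors the 7-day window in Table 6.2 and which date ends the treatment period for the PPS 52-week rule.

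The cost is SAP wording and a small programming change, since the date is already collected. Reported exposure becomes slightly shorter. Computed compliance rises slightly for discontinued subjects, so a subject just under the 75% limit could remain in the PPS.
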